Criteria for evaluation: Primary endpoints: 
Proportion of patients with $\geq 5\%$ reduction from baseline in BMI after 16 weeks of setmelanotide treatment compared to a historic control of $< 5\%$ in this patient population. Key Secondary Endpoints: 
Composite proportion of patients aged ≥ 6 to < 18 years with ≥ 0.2 reduction of BMI Z-score and patients aged ≥ 18 years with 5% reduction of body weight from baseline after 16 weeks of setmelanotideProportion of patients aged ≥ 6 to < 18 years with ≥ 0.2 reduction of BMI Z-score from baseline after 16 weeks of setmelanotideProportion of patients aged ≥ 18 years with $\geq 5\%$ reduction of body weight from baseline after 16 weeks of setmelanotide Other Secondary Endpoints: 
Change from baseline in waist circumference in patients aged ≥ 18 years after 16 weeks of setmelanotide treatment.Change in hunger in response to 16 weeks of setmelanotide treatment as measured by change from baseline in daily and global hunger scores.Safety and tolerability assessed by the frequency and severity of AEs, vital signs, and laboratory evaluations.  Statistical methods: The study is a Phase 2, Proof-of-Concept study. The objective of this study is to evaluate safety and preliminary efficacy on weight loss in patients with HO. The primary endpoint is the proportion of patients who achieve at least 5% reduction from baseline in BMI at ~16 weeks of treatment with setmelanotide. Given the exploratory nature of the study, the sample size is primarily driven by clinical considerations, with the consideration of statistical testing. It is planned to enroll ~5 to 10 patients aged ≥ 12 years, and up to 10 patients between 6 and < 12 years. With 10 patients aged ≥ 12 years and up to

Name of Sponsor/Company: Rhythm Pharmaceuticals, Inc.
Name of Investigational Product: Setmelanotide
Name of Active Ingredient: Setmelanotide (RM-493; Melanocortin-4 Receptor Agonist)
10 patients aged 6 to <12 years, at 1-sided 0.05 significance level, the study provides ~90% power to reject the null hypothesis that the true response rate is less than 5%, assuming a 40% target response rate in setmelanotide.

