5. STUDY DESIGN

5.1. Overall Design

This is a Phase 2, multicenter, open-label, proof of concept study designed to assess the effect of setmelanotide on weight loss on a population affected by HO. Approximately 15 patients aged 6 to 40 years, inclusive, are planned to be enrolled across approximately 3-5 clinical sites in the United States (US).

Screening Period

Upon providing informed consent, patients will enter the Screening Period, during which they will be assessed for eligibility and complete all screening procedures as described in the Schedule of Activities (SoA) ([Table 1](#)).

Treatment Period

Patients who are determined to be eligible, based on Screening assessments, will return to the clinic for the Baseline Visit (Visit 2) and receive the first setmelanotide dose. The starting setmelanotide dose is dependent on patient age; however, for all patients, the setmelanotide dose will be titrated to a final dose of 3.0 mg/day (initial titration phase), as follows:

Patients aged 6 to <16 years, inclusive

- Starting at Baseline (Day 1; Visit 2) through approximately Day 14, patients will receive setmelanotide 1.0 mg/day.
- Starting at approximately Day 15 through 28, patients will receive setmelanotide 2.0 mg/day.
Patients/caregivers will be contacted by study center personnel on Day 15 to ensure dose titration has occurred and to document any AEs.
- Starting on approximately Day 29 (Visit 3), patients will receive setmelanotide 3.0 mg/day; patients will continue to receive setmelanotide 3.0 mg/day for 12 weeks.

The dose of setmelanotide should be titrated as explained in the SoA.

Patients aged ≥16 years, inclusive

- Starting at Baseline (Day 1; Visit 2) through approximately Day 14, patients will receive setmelanotide 2.0 mg/day.
- Starting at approximately Day 15, patients will receive setmelanotide 3.0 mg/day; patients will continue to receive setmelanotide 3.0 mg/day for 14 weeks.

Patients/caregivers will be contacted by study center personnel on Day 15 to ensure dose titration has occurred and to document any AEs.

The dose of setmelanotide should be titrated as explained in the SoA.

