6.1. Inclusion Criteria

Patients must meet all of the following criteria to be eligible for study participation:

1. Patient has documented evidence of HO, including:
 - a. Recent (within the previous 8 months before Screening) evidence of hypothalamic injury on magnetic resonance imaging (MRI); AND
 - b. Diagnosis of craniopharyngioma or other non-malignant brain tumor affecting the hypothalamic region; AND
 - c. Has undergone surgery, or chemotherapy, or radiation ≥ 6 months and ≤ 15 years before Screening.
2. Patient has either unilateral hypothalamic lesions (at least 6 patients) or bilateral hypothalamic lesions (at least 7 patients), as assessed by MRI.

Note: Although the intention of the study is to enroll at least 6 patients with unilateral hypothalamic lesions, the Sponsor may decrease the required number during the course of the study.
3. Aged 6 to 40 years, inclusive, at time of enrollment. (A maximum of 10 patients between the ages of 6 and 12 will be enrolled in the study.)

4. Obesity, documented by a BMI $\geq 35 \text{ kg/m}^2$ for patients ≥ 18 years of age or BMI $\geq 95^{\text{th}}$ percentile for age and gender for patients 6 to <18 years of age based on the US Centers for Disease Control and Prevention criteria.
5. Documented increase in BMI (change from pre-surgery baseline in BMI Z-score ≥ 0.2 for patients <18 years of age or BMI $>5\%$ for patients ≥ 18 years of age) either during the first 6 months following surgery or within 1 year before surgery AND still present at Screening.
6. More than 6 months after the end of post-tumor treatment, including chemotherapy, surgery, or radiation.
7. Patient must meet one of the following contraception requirements:
 - If a female of childbearing potential, defined as fertile, following menarche and until becoming post-menopausal unless permanently sterile (hysterectomy, bilateral salpingectomy, or bilateral oophorectomy), must use a highly effective form of contraception as outlined in Section 9.19.5.
 - If a female of non-childbearing potential, defined as permanently sterile (status post hysterectomy, bilateral oophorectomy, or bilateral salpingectomy) or post-menopausal for at least 12 months (and confirmed with a screening follicle-stimulating hormone [FSH] level in the post-menopausal laboratory range), contraception is not required during the study.

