10.1. Sample Size Determination

The study is a Phase 2, Proof-of-Concept study. The objective of this study is to evaluate safety and preliminary efficacy on weight loss in patients with HO. The primary endpoint is the proportion of patients who achieve at least 5% reduction from baseline in BMI at ~16 weeks of treatment with setmelanotide. Given the exploratory nature of the study, the sample size is primarily driven by clinical considerations, with the considerations of statistical testing. It is planned to enroll ~5 to 10 patients aged >12 years, and up to 10 patients between 6 and 12 years. With 10 patients aged >12 years and up to 10 patients aged 6 to 12 years, at 1-sided 0.05 significance level, the study provides ~90% power to reject the null hypothesis that the true response rate is less than 5%, assuming a 40% target response rate in setmelanotide.

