10.3. Statistical Analyses

A separate statistical analysis plan will be developed, which will include a more technical and detailed description of the statistical analyses described in this section. This section is a summary of the planned statistical analyses of the most important endpoints including primary and other endpoints

The primary endpoint is defined as the proportion of patients who achieve at least 5% BMI reduction from baseline, at ~16 weeks of treatment with setmelanotide. The primary statistical hypothesis will be tested with an exact binomial test at 1-sided 0.05 significant level, compared to a historical control rate of 5%. The 2-sided 90% Clopper-Pearson confidence interval will be provided.

For the primary endpoint, and all other endpoints, the last value obtained prior to the first dose of active treatment will be considered the baseline value for statistical analyses.

AEs will be coded by using the most current version of Medical Dictionary for Regulatory Activities and summarized by system organ class, preferred term, and treatment group for the number and percent of AEs reported, the number of patients reporting each AE, and the number of patients with any AE.

A by-patient AE data listing including onset and resolution dates, verbatim term, preferred term, treatment, severity, relationship to treatment, action taken, and outcome will be provided.

Safety data including laboratory evaluations and vital signs assessments will be summarized by time of collection and by treatment group. In addition, change from baseline to any post-dose values will be summarized for vital signs and clinical laboratory results. Frequency of patients with abnormal safety laboratory results will be tabulated by treatment.

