### 3.4 Determination of Sample Size

The objective of this study is to evaluate safety and preliminary efficacy on weight loss in patients with HO. The primary endpoint is the proportion of patients who achieve at least 5% BMI reduction from baseline at ~16 weeks of treatment with setmelanotide. Given the exploratory nature of the study, the sample size is primarily driven by clinical considerations, with the considerations of statistical testing. It is planned to enroll ~5-10 patients aged >12 years, and up to 10 patients between 6 and 12 years. With 10 patients aged >12 years and up to 10 patients aged 6 to 12 years, at 1-sided 0.05 significance level, the study provides ~90% power to reject the null hypothesis that the true response rate is less than historical control rate of 5%, assuming a 40% target response rate in setmelanotide.

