## 9.1 Primary Efficacy Endpoint

The primary endpoint is defined as the proportion of patients who achieve at least 5% BMI reduction from baseline, at ~16 weeks of treatment with setmelanotide. BMI will be calculated using patient's weight and height assessments, using the following formula:

$$BMI = \frac{kg}{m^2}$$

If needed, weight and height will first be converted into kilograms and meters, respectively. Given that body weight is collected in triplicates at each visit, weight (kg) will first be aggregated into one averaged weight per visit. Visits will then be compared against the analysis visit window (described in [Section 4.2](#)) to select the Week 16 averaged weight prior to calculating BMI and change in BMI. Patients who are  $\geq 18$  years of age will only have height measurement done at screening; the averaged triplicate

screening height will be used for the height component of the BMI calculation at each visit. Patients who are < 18 years of age will have their height measured in triplicates at most study visits. As with body weight, height will first be aggregated into one averaged height per visit and compared against the analysis visit window to select the Week 16 averaged height. Regardless of reason, if height is missing for an analysis visit, then height will be imputed using last observation carried forward (LOCF). Change ( $\Delta$ ) in BMI (%) from baseline at 16 weeks of treatment will be calculated as follows:

$$\Delta \text{ BMI } (\%) = \left( \frac{\text{Week 16 BMI} - \text{Baseline BMI}}{\text{Baseline BMI}} \right) * 100$$

An indicator variable will then be created to identify patients that have a decrease in BMI from baseline to Week 16 of 5% or more, allowing for the analysis of proportion of patients who achieve at least 5% BMI reduction.

The primary endpoint will be assessed using an exact binomial test at a 1-sided 0.05 significant level, compared to the null hypothesis proportion of 0.05 (which comes from a historical control rate of 5%). The number of and the binomial proportion of patients who achieve at least 5% BMI reduction from baseline at 16 weeks, the corresponding 2-sided 90% CI, and one-sided binomial test p-value will be presented. The Clopper-Pearson method will be used to calculate the CI. A scatter plot figure will also be created plotting each patient's percent BMI reduction from baseline to Week 16.

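### The stated power of about 90% is not the power of the planned exact test at 15 patients (97.3%), nor at 10 (83.3%) or 20 (98.4%)

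*Protocol*

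**What the plan says.** Three places give the same power figure for a 5% null rate and a 40% target rate at one-sided 0.05:

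- Protocol 10.1: "the study provides ~90% power to reject the null hypothesis that the true response rate is less than 5"%.
- Protocol synopsis, statistical methods: "the study provides ~90% power".
- SAP 3.4: "the study provides ~90% power to reject the null hypothesis that the true response rate is less than historical control rate of 5"%.

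Each attaches the figure to 10 patients in the older age group and up to 10 in the younger one, so the total could be anything from 10 to 20. No single total appears in the sentence. Protocol 5.1 gives the enrolment plan: "Approximately 15 patients aged 6 to 40 years, inclusive, are planned to be enrolled". Protocol 5.2 and SAP 3.2 and 3.2.1 also say about 15.

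The test is specified consistently. Protocol 10.3 has the primary hypothesis "tested with an exact binomial test at 1-sided 0.05 significant level", and SAP 9.1 has it "assessed using an exact binomial test at a 1-sided 0.05 significant level, compared to the null hypothesis proportion of 0.05". Both pair it with a two-sided 90% Clopper-Pearson interval.

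Inclusion criterion 2 in Protocol 6.1 sets lesion minimums: "Patient has either unilateral hypothalamic lesions (at least 6 patients) or bilateral hypothalamic lesions (at least 7 patients), as assessed by MRI". A note lets the Sponsor lower the unilateral number.

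**The concern.** Every input to a power calculation is given except the sample size, and the obvious candidates for it do not return 90%. The sentence is the only quantitative statistical support for the study size. As written, a reader cannot tell which total it describes, how many responders would reject the null, or what the real error rates are.

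The implied chance of missing a true 40% response rate is about 10%. Under the planned test it is 2.7% with 15 patients and 16.7% with 10. The figure therefore undersells the design at its planned size and oversells it at the low end of the sentence's own range.

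**Working it through.** **Inputs**

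| Input | Value | Source |
|---|---|---|
| Test | Exact binomial, one-sided 0.05 | Protocol 10.3, SAP 9.1 |
| Null rate | 0.05 | Protocol 10.3, SAP 9.1 |
| Target rate | 0.40 | Protocol 10.1, SAP 3.4 |
| Total in the power sentence | 10 to 20 | Protocol 10.1, SAP 3.4 |
| Planned enrolment | about 15 | Protocol 5.1 and 5.2, SAP 3.2 |
| Dropout allowance | none stated | – |

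**Formula.** With X the number of responders among n patients, the critical value c is the smallest integer with P(X ≥ c | n, 0.05) ≤ 0.05. The attained alpha is that probability, and power is P(X ≥ c | n, 0.40).

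**Trying to reproduce 90%.** Under the stated test, only two totals come close: n = 11 gives 88.1% and n = 12 gives 91.7%. The planned total does not.

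**n = 15**

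- P(X ≥ 2 | 0.05) = 0.171, above 0.05. P(X ≥ 3 | 0.05) = 0.0362. So c = 3.
- Power = 1 − [0.6^15 + 15(0.4)(0.6^14) + 105(0.4^2)(0.6^13)] = 1 − (0.0005 + 0.0047 + 0.0219) = 0.973.

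**n = 10**

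- P(X ≥ 2 | 0.05) = 0.0861, above 0.05. P(X ≥ 3 | 0.05) = 0.0115. So c = 3.
- Power = 1 − (0.0060 + 0.0403 + 0.1209) = 0.833.

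**n = 20**

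- P(X ≥ 3 | 0.05) = 0.0755, above 0.05. P(X ≥ 4 | 0.05) = 0.0159. So c = 4.
- Power = P(X ≥ 4 | 0.40) = 0.984.

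**The whole range**

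| n | Responders needed | Attained alpha | Exact power |
|---|---|---|---|
| 10 | 3 | 0.0115 | 83.3% |
| 11 | 3 | 0.0152 | 88.1% |
| 12 | 3 | 0.0196 | 91.7% |
| 13 | 3 | 0.0245 | 94.2% |
| 14 | 3 | 0.0301 | 96.0% |
| 15 | 3 | 0.0362 | 97.3% |
| 16 | 3 | 0.0429 | 98.2% |
| 17 | 4 | 0.0088 | 95.4% |
| 18 | 4 | 0.0109 | 96.7% |
| 19 | 4 | 0.0132 | 97.7% |
| 20 | 4 | 0.0159 | 98.4% |

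The lesion minimums in criterion 2 add to 6 + 7 = 13 unless the unilateral one is lowered. From 13 to 20 patients the exact power never drops below 94.2%.

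**Where 90% might have come from.** These are possibilities only:

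- The arcsine approximation at n = 10, one-sided 0.05: Φ(h√n − 1.645) with h = 2·asin√0.40 − 2·asin√0.05 = 0.918, giving 89.6%.
- The continuity-corrected normal approximation at n = 10, one-sided 0.05: 88.6%.
- The exact test at one-sided 0.025 with n = 15: at least 4 responders needed, attained alpha 0.0055, power 90.9%.

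At one-sided 0.05 the first two approximations give 97.2% and 96.2% at n = 15, so they do not explain the figure at the planned size.

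**The case against.** The strongest reply has four parts.

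- **The sentence covers a range, and 90% lies within it.** Exact power runs from 83.3% to 98.4% over 10 to 20 patients, so no single rounded figure could fit both ends. This is fair, and it means one cannot say that no total gives 90%. But 11 and 12 are planned nowhere.
- **The figure may have been computed at one-sided 0.025.** With 15 patients that gives 90.9%, the closest match at the planned size. The SAP does use two-sided 5% conventions elsewhere: the general interval convention in section 4 and the 95% interval for pooled imputation results in 16.5. This is a live explanation of the source, but not a defence of the text. Every statement about the power or the primary test says one-sided 0.05, with a matching 90% interval.
- **The analysed number may be smaller than 15.** Twelve evaluable patients would give 91.7%. The documents state no such allowance, and SAP 11.1 carries the last observation forward for missing Week 16 data in the primary analysis. SAP 9.1 can be read as putting an observed-data analysis first, so some loss is conceivable, but it would be an added assumption.
- **The study is exploratory and its size is mainly clinically driven.** That is what the plan says, and it limits the consequences. It does not make the stated power correct.

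**Conclusion.** The concern holds. The stated power is not that of the planned test at the planned size: it is about 7 points too low at 15 patients, 8 too low at 20 and 7 too high at 10. This rests on the plan's own inputs (exact binomial, one-sided 0.05, 5% versus 40%) and on all enrolled patients being analysed. The source of the figure cannot be established from the documents.

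The effect is modest. Within the 10 to 20 range, power is below 90% only at 10 or 11 patients. At about 15 the error is in the safe direction, and nothing in the analysis or the enrolment plan turns on it. It should still be corrected, because it is a wrong statement of the design's properties repeated in three places.

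**What to change.** In the synopsis, Protocol 10.1 and SAP 3.4, replace the power sentence with one that names the total, the critical count, the attained alpha and the exact power. For example: With 15 patients, the exact test at one-sided 0.05 rejects if at least 3 respond (attained alpha 0.036) and has 97% power at a 40% response rate. With 10 patients the power is 83% (at least 3 responders), and with 20 it is 98% (at least 4).

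If the original figure came from a different total, alpha, evaluability assumption or approximation, state which. Leave the one-sided 0.05 level and the 90% confidence interval as they are. The cost is a wording change in three places, with no extra patients and no change to the analysis.

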10.2. Populations for Analyses

There are 3 analysis population defined in the protocol:

- Full Analysis Set: All patients who received at least 1 dose of setmelanotide and have baseline data.
- Per-Protocol Set: All patients in FAS without any major protocol violations that will result in exclusion of the patients from the analysis
- Safety Analysis Set: All patients who received at least 1 dose of study drug.

10.3. Statistical Analyses

A separate statistical analysis plan will be developed, which will include a more technical and detailed description of the statistical analyses described in this section. This section is a summary of the planned statistical analyses of the most important endpoints including primary and other endpoints

The primary endpoint is defined as the proportion of patients who achieve at least 5% BMI reduction from baseline, at ~16 weeks of treatment with setmelanotide. The primary statistical hypothesis will be tested with an exact binomial test at 1-sided 0.05 significant level, compared to a historical control rate of 5%. The 2-sided 90% Clopper-Pearson confidence interval will be provided.

For the primary endpoint, and all other endpoints, the last value obtained prior to the first dose of active treatment will be considered the baseline value for statistical analyses.

AEs will be coded by using the most current version of Medical Dictionary for Regulatory Activities and summarized by system organ class, preferred term, and treatment group for the number and percent of AEs reported, the number of patients reporting each AE, and the number of patients with any AE.

A by-patient AE data listing including onset and resolution dates, verbatim term, preferred term, treatment, severity, relationship to treatment, action taken, and outcome will be provided.

Safety data including laboratory evaluations and vital signs assessments will be summarized by time of collection and by treatment group. In addition, change from baseline to any post-dose values will be summarized for vital signs and clinical laboratory results. Frequency of patients with abnormal safety laboratory results will be tabulated by treatment.

10.3.1. Interim Analyses

There is no planned interim analysis for the purposes of modifying the study.

12. APPENDICES

APPENDIX 1. ABBREVIATIONS AND TRADEMARKS

Abbreviation	Definition
AE	Adverse event
ALT	Alanine aminotransferase
ARC	Arcuate nucleus
AST	Aspartate aminotransferase
BMI	Body mass index
BP	Blood pressure
CFR	Code of Federal Regulations
CIOMS	Council for International Organizations of Medical Sciences
CMHL	Combined medial hypothalamic lesion
COVID-19	Coronavirus Disease 2019
C-SSRS	Columbia-Suicide Severity Rating Scale
CTCAE	Common Terminology Criteria for Adverse Events
CV	Cardiovascular
DXA	Dual-energy X-ray absorptiometry
ECG	Electrocardiogram
eCRF	Electronic case report form
EOS	End-of-Study
EQ-5D	EuroQol-5 Dimension
GCP	Good Clinical Practice
GFR	Glomerular filtration rate
GLP-1	Glucagon-like peptide-1
HDL	High-density lipoprotein
HO	Hypothalamic obesity
HR	Heart rate
ICF	Informed consent form
ICH	International Council for Harmonisation
IRB	Institutional Review Board
IUD	Intrauterine device
IWQOL-Lite-CT	Impact of Weight on Quality of Life-Lite Clinical Trials Version

Abbreviation	Definition
LEPR	Leptin receptor
MC4R	Melanocortin 4 receptor
MDD	Major Depressive Disorder
MHP	Mental health professional
mPEG/DSPE	N-[Carbonyl-methoxypolyethylene glycol 2000]-1,2-distearoyl-glycero-3-phosphoethanolamine sodium salt
MRI	Magnetic resonance imaging
MSH	Melanocortin stimulating hormone
NHLBI	National Heart, Lung, and Blood Institute
PGIC	Patient global impression of change
PGIS	Patient global impression of severity
PHQ	Patient Health Questionnaire
POMC	Proopiomelanocortin
PVN	Paraventricular nucleus
QD	Once daily
RBC	Red blood cell
RR	Respiration rate
SAE	Serious adverse event
SAP	Statistical analysis plan
SC	Subcutaneous(ly)
SF	Short Form
SoA	Schedule of Activities
SUSAR	Suspected unexpected serious adverse reaction
TEAE	Treatment-emergent adverse event
US	United States
VMN	Ventromedial nucleus of the hypothalamus
WOCBP	Woman of childbearing potential

